#### **12.3.2.2. Expedited Reporting by Sponsor**

The sponsor and/or designee will report all **serious adverse events and unexpected events with a reasonable possible causality to the investigational product** as judged by either the investigator or the sponsor to the relevant parties within the stipulated timelines.

SAEs will be considered reportable regardless of whether or not the investigational product was used in accordance with the provisions in the protocol, Investigator's Brochure and labeling.

### **12.4. Follow-up of Adverse Events and Serious Adverse Events**

#### **12.4.1. Follow-up of Adverse Events with Onset during the Study**

During the study, the investigator and/or designee must follow-up on each AE until it is resolved or until the medical condition of the subject is stable.

After the subject's last visit, the investigator and/or designee must follow-up on any AE classified as serious or considered to have a reasonable possible causality to the investigational product until it is resolved or until the medical condition of the subject is stable. All such relevant follow-up information must be reported to the sponsor and/or designee. If the event is a chronic condition, the investigator and sponsor may agree that further follow-up is not required.

#### **12.4.2. Collection of Serious Adverse Events with Onset after Last Study Visit**

If an investigator and/or designee become aware of an SAE after the subject's last visit, and s/he assesses the SAE to have a reasonable possible causality to the investigational product, the case will have to be reported to the sponsor and/or designee, regardless how long after the end of the study this takes place.

#### **12.4.3. Tissue Explant and Histology**

If the study product or a segment of native vessel or any other tissue is removed for any reason during the course of the study, the explanted tissue and/or product will be sent for histopathological and microbiological analysis. In the event of an explant, the investigator and/or designee must follow expedited reporting procedures outlined in Section 12.3.2 for SAEs.

### **12.5. Data and Safety Monitoring Board**

The Data and Safety Monitoring Board (DSMB) will:

- Evaluate safety of enrolled subjects at periodic intervals (at least every six months),
- Review the final Clinical Study Report, at the conclusion of the study.

## **13. STATISTICS**

### **13.1. Statistical Analysis Plan**

The content of this section is the basis for the Statistical Analysis Plan (SAP) of this study. The SAP provides full details of the analyses, data displays, and algorithms to be used for data derivations. The SAP includes the definition of major and minor protocol deviations and the link between major protocol deviations and the analysis sets. Medically trained staff will identify major and minor protocol deviations before study closure.

### **13.2. Determination of Sample Size**

All power calculations are via EAST® 6.4. Assuming the TRUE underlying FSD6 rates are 45% for control and 76% for treatment (based on prior data), the sample size on N=200 patients contributing to the analysis has >99% power to yield a statistically significant (alpha=0.05 2-

sided) difference between treatments. Allowing for uncertainty in the prior data, if the TRUE underlying FSD6 rates are 45% and 65%, there is approximately 82% power. The minimum OBSERVED difference that would yield statistical significance is approximately 45% vs 59%.

### **13.3. Data Analysis Considerations**

#### **13.3.1. Analysis Sets**

##### **13.3.1.1. Full Analysis Set**

The full analysis set will consist of all subjects who are randomized to treatment or control. Full details are provided in the SAP.

##### **13.3.1.2. Safety Set**

The safety set will consist of all subjects who are enrolled in the study, i.e., run-in subjects plus subjects who are randomized to treatment or control. Full details are provided in the SAP.

#### **13.3.2. Key Endpoints**

The primary endpoint is FSD6, as defined in Section 6. Each endpoint will be tested at overall alpha level of 0.05 (2-sided). Other efficacy endpoints are as mentioned in the endpoints section (Section 6).

#### **13.3.3. Main Analysis**

The null hypothesis for FSD6 is that the population proportions of subjects with FSD6 for the treatment group receiving the sirolimus eluting collagen implant [ $p_I$ , where “I” indicates implant treatment] and the control group ( $p_C$ , where “C” indicates control group) that does not receive the implant are equal. The alternative is that the proportion of subjects with FSD6 is not equal for the treatment group and the control group.

Algebraically, these hypotheses are stated as follows, where “H0” indicates the null hypothesis and “Ha” indicates the alternative hypothesis:

$$H0: p_I = p_C$$

$$Ha: p_I \neq p_C$$

“I” indicates implant treatment, and “C” indicates control treatment.

For the primary endpoint of FSD6, the proportions will be compared between treatment and control using a logistic regression model with factors for treatment and stratum.

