## 2. SYNOPSIS

Name of Sponsor: Vascular Therapies, Inc.	
Name of Investigational Product: Sirolimus-eluting Collagen Implant (SeCI)	
Name of Active Ingredient: Sirolimus	
Title of Study: A Phase 3, Randomized, Multicenter, Single-blind, Controlled Study evaluating Arteriovenous fistula outcomes with and without a Perivascular Sirolimus-eluting Collagen Implant (The ACCESS Trial)	
Study center(s): Approximately 20 centers in the United States will participate in this study.	
Studied period (years): Estimated date first patient enrolled: 01 Nov 2015 Estimated date last patient completed: 30 Jun 2019	Phase of development: 3
Study Objectives and Hypothesis: The objective of this study is to evaluate efficacy and safety outcomes following use of the Sirolimus-eluting Collagen Implant in subjects undergoing surgical creation of an AV fistula for vascular access (index procedure). Following successful creation of the AV fistula, the cohort randomized to the treatment group will receive the SeCI; the control group will not receive an implant. The primary study hypothesis is that the proportion of subjects that meet requirements for fistula suitability for dialysis, six months following the index procedure, will be higher in the treatment group in comparison to the control group.	

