Methodology: This is a randomized, single blind, multicenter study designed to evaluate the efficacy and safety of the SeCI in subjects who are on hemodialysis or are preparing for hemodialysis and are undergoing surgery for creation of a new AV fistula. Subjects will be randomized 1:1 to the treatment group or control group. Subjects randomized to the treatment group will receive the investigational product; subjects randomized to the control group will undergo AV fistula surgery without implantation of the investigational product. Randomization will be stratified by surgeon and fistula location (radiocephalic or brachiocephalic); at least 80% of the randomized subjects will receive a radiocephalic fistula and at most 20% of the subjects will receive a brachiocephalic fistula. The randomization scheme will be monitored and controlled via the IVR/IWR system.  The first subject enrolled by each participating surgeon will be a “run-in subject”, not part of the randomized subject set. “Run-in subjects” will undergo surgery for the creation of an AV fistula and receive the SeCI. This is to familiarize the investigators with the SeCI implant procedure. Enrolled subjects will be followed for a period of one year from the time of their index procedure.	
Number of patients (planned): Planned enrollment is approximately 240 subjects. Approximately 220 subjects are planned to be randomized in equal proportions to treatment and control to yield approximately 200 evaluable subjects. The randomized cohort will include a minimum of 100 evaluable subjects who are on hemodialysis at the	

time of the index procedure.

In addition to the 220 randomized subjects, approximately 20 run-in subjects will be enrolled.

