#### **Data Analysis and Statistical methods:**

The data will be summarized in tables by treatment group, and will list the mean, standard deviation, median, minimum, maximum, and number of subjects in a group for continuous data; count and percentage for categorical data; and median, 25th and 75th percentiles, relative risk and 95% confidence intervals for time-to-event data. Data will be listed for each subject. Statistical analyses will be performed and data appendices will be created using SAS.

The efficacy analysis will be conducted on the full analysis set. The full analysis set will consist of all randomized subjects who received vascular access surgery (**NOTE: The run-in patient at each site will be excluded from the full analysis set but will be included in the safety set**). The primary efficacy endpoint is Fistula Suitability for Dialysis at 6 months (FSD6) This endpoint will be analyzed using logistic regression with factors for treatment and stratum. The treatment effect will be tested at overall

alpha=0.05, 2-sided, to compare the proportions of patients between treatments.

Time to event secondary endpoints will be analyzed via stratified log rank test. Binary endpoints will be compared between treatments via the same logistic regression model as for the primary endpoint.

Continuous secondary endpoints will be compared via analysis of covariance for a model including treatment, strata, and baseline covariate if measured at baseline, or non-parametric rank tests if normality or homogeneity assumptions appear substantially violated. Endpoints will be tested for statistically significant difference between treatments, each at alpha=0.05, 2-sided.

Summary statistics for demographics and important baseline parameters will be provided by treatment group and for all subjects combined. TEAE's and SAE's will be summarized by counts and proportions by treatment for each body system organ class and by preferred term within class.

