## 7. INVESTIGATIONAL PLAN

### 7.1. Overall Study Design

This is a Phase 3, multicenter, randomized, single blind, controlled, adaptive study designed to evaluate the efficacy and safety of the use of the Sirolimus-eluting Collagen Implant (SeCI) in subjects who are on hemodialysis or are preparing for hemodialysis and are undergoing surgical creation of an AV fistula in comparison to subjects who do not receive the implant.

Subjects of either gender, who are at least 18 years of age, undergoing hemodialysis or are expected to initiate hemodialysis within 6 months of study enrollment, and require a new single-stage radiocephalic or brachiocephalic end-to-side fistula will be eligible to participate in this study. It is expected that all subjects will be enrolled across approximately 20 sites and each enrolled subject will be followed for one year from the time of fistula creation.

Subjects who meet eligibility criteria and undergo successful AV fistula creation will be eligible for enrollment. The study plans to enroll approximately 240 subjects. Of these, the first subject enrolled by a participating surgeon will be a run-in subject; run-in subjects will not be part of the randomized set; all run-in subjects will receive the SeCI. The intent of enrolling run-in subjects in the clinical study is to familiarize the investigators with the implant procedure. Approximately 220 subjects will be randomized in a 1:1 ratio using permuted block randomization stratified by surgeon and fistula location (radiocephalic or brachiocephalic) to yield approximately 200 evaluable subjects. The randomized cohort will include a minimum of 100 evaluable subjects who are on hemodialysis at the time of the index procedure.

Subjects who are on hemodialysis at the time of enrollment will undergo evaluations to determine fistula suitability for cannulation starting no earlier than day 28 post index procedure; the frequency of assessments for cannulation suitability will be at the discretion of the investigator and/or designee. The decision to proceed with first cannulation will be made by the investigator based on clinical assessment of the fistula. In addition, subjects who have not initiated hemodialysis by:

- Day 90 post index procedure, and the index fistula has not been abandoned, a vascular ultrasound will be performed at the 3 month follow up visit,

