### **9.2.2.1. Run-in Subjects**

The first subject eligible for enrollment under each participating surgeon at each investigational site in the study will receive the SeCI. The designated surgical study coordinator will break the tamper evident seals, the surgical team will prepare the product per instructions provided in the Instructions for Use (see [Appendix C](#)), and the surgeon will implant the investigational product.

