### **9.2.2.2. Randomization**

Following successful creation of an AV fistula, subjects will be randomized in a 1:1 ratio to treatment or control using permuted block randomization stratified by surgeon and fistula location (radiocephalic / brachiocephalic). At least 80% of the subjects randomized will receive a radiocephalic fistula and at most 20% of the randomized subjects will receive a brachiocephalic fistula. The above randomization scheme will be applicable to subjects on hemodialysis at the time of enrollment or not on hemodialysis at the time of enrollment separately. The randomization scheme will be monitored and controlled via the IVR/IWR system.

The designated surgical study coordinator will contact the IVR/IWR System to receive the randomization code and treatment assignment for the subject.

- If the subject is randomized to the treatment group, the designated surgical study coordinator will break the tamper evident seals, the surgical team will prepare the product per instructions provided in the Instructions for Use (see [Appendix C](#)), and the surgeon will implant the investigational product.
- If the subject is randomized to the control group, the surgeon will complete the surgery per standard practice, (without implanting the investigational product). The designated surgical study coordinator will ensure that the tamper evident seals on the investigational product packaging have not been broken and will return the investigational product to inventory.

Following completion of surgery, the designated surgical study coordinator will confirm using the IVR/IWR System that:

- the surgical procedure was successfully completed, and,
- the randomization number was used

Once a randomization number has been used, it will not be re-used. Authorized study personnel will ensure that the assigned randomization number is recorded in the subject's source document.

Upon completion of the index procedure, the surgical incision will be closed according to the surgeon's standard practice.

If the subject is randomized to the control group, the designated surgical study coordinator will ensure that the tamper evident seal on the component membrane packaging has not been broken and will return the investigational product to inventory.

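### The primary logistic model does not define its stratum; if each surgeon-by-location cell gets its own unconditional fixed effect, two-sided type I error is about 7% instead of 5%

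*Combined protocol and SAP*

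**What the plan says.** Section 13.3.3 specifies that "the proportions will be compared between treatment and control using a logistic regression model with factors for treatment and stratum". The synopsis repeats it: "This endpoint will be analyzed using logistic regression with factors for treatment and stratum". Section 13.3.2 sets the level at 0.05, two-sided. Section 13.3.4 applies the same model to the binary secondary endpoints, which are suitability at 12 months and maturation by day 90.

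The word stratum is otherwise explained only for randomization. Section 7.1 describes allocation "using permuted block randomization stratified by surgeon and fistula location (radiocephalic or brachiocephalic) to yield approximately 200 evaluable subjects". Section 9.2.2.2 adds: "The above randomization scheme will be applicable to subjects on hemodialysis at the time of enrollment or not on hemodialysis", each group separately, so dialysis status may be a third stratifier.

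The number of surgeons is not stated. Section 7.1 says that "the first subject enrolled by a participating surgeon will be a run-in subject", and section 9.2.2.1 that "The first subject eligible for enrollment under each participating surgeon at each investigational site in the study will receive the SeCI". The synopsis gives the counts: "In addition to the 220 randomized subjects, approximately 20 run-in subjects will be enrolled" and "Approximately 20 centers in the United States will participate in this study".

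Section 13.1 refers to the SAP for full analysis detail. The text available for review contains no SAP wording that defines the stratum or the form of the fit.

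**The concern.** Logistic regression with one intercept per stratum works when strata are large. When they hold only a few subjects each, ordinary (unconditional) maximum likelihood pushes the treatment log odds ratio away from zero and understates the variance of the test statistic, so the test rejects too often. Twenty or so surgeons crossed with two locations, for 200 subjects, is in that range.

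The most direct literal reading of the model, with the randomization strata as the stratum factor, would therefore miss the level set in section 13.3.2. It would also report too large an odds ratio, for the primary endpoint and for two secondary endpoints in the step-down sequence. Other readings of the same sentence would not. The choice affects both the p-value and the estimate, so it should not be open once treatment codes are known.

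**Working it through.** **1. The plan's own figures.** With 100 per arm and a pooled two-proportion z-test:

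- 45% vs 65%: (0.20 − 1.96 × √(2 × 0.55 × 0.45/100)) / √(0.45 × 0.55/100 + 0.65 × 0.35/100) = (0.20 − 0.1379)/0.0689 = 0.90, so power is 81.6%. The plan says about 82%.
- 45% vs 76%: the same formula gives 99.6%. The plan says above 99%.
- 45% vs 59% observed: 0.14/√(2 × 0.52 × 0.48/100) = 1.98, significant. 45% vs 58% gives 1.84, not significant.

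All three reproduce, as an unstratified comparison.

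**2. Number of cells.** One run-in per surgeon and about 20 run-ins suggest about 20 surgeons. With subjects spread at random over surgeons and 20% brachiocephalic (the plan's maximum), practically all 20 radiocephalic cells are occupied. The expected number of occupied brachiocephalic cells is 20 × [1 − (1 − 0.20/20)^200] = 20 × (1 − 0.134) = 17.3. The total is 37.3 cells, or 200/37.3 = 5.4 subjects per cell. About 26 cells carry information on treatment.

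**3. Why the test over-rejects.** Take a cell with n subjects, n₁ treated, n₀ control, m₁ responders and m₀ non-responders. The unconditional and conditional score tests share the same numerator, observed minus n₁m₁/n. They differ in variance:

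- conditional (CMH): n₁n₀m₁m₀ / [n²(n − 1)]
- unconditional: n₁n₀m₁m₀ / n³

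The unconditional variance is too small by the factor (n − 1)/n in each cell. In simulation under the step 4 assumptions, the ratio of the summed variances averages about 1.18 with 20 surgeons. The implied type I error is 2[1 − Φ(1.96/√1.18)] = 2[1 − Φ(1.80)] ≈ 7%. The ratio is about 1.10 with 10 surgeons (about 6%) and about 1.32 with 40 (about 9%).

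**4. Simulation.** Base assumptions: 200 subjects, permuted blocks of 4 within cells, 20% brachiocephalic, 45% response in both arms, nominal two-sided 5%. Ranges cover Wald, likelihood-ratio and score tests over several independent runs of 6,000 to 40,000 replicates.

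| One unconditional fixed effect per cell | Type I error |
|---|---|
| 10 surgeons | about 6% |
| 15 surgeons | 6.5–6.7% |
| 20 surgeons | about 7% (6.6–7.7%) |
| 30 surgeons | 7.6–8.2% |
| 40 surgeons | 8–9.5% |
| 20 surgeons, dialysis status crossed | 8.5–9.3% |

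The 20-surgeon range includes uneven surgeon volumes, blocks of 2 and surgeon variation up to SD 0.7 on the logit scale. With 10% brachiocephalic fistulas it is 6.5–6.7%, and with none 6.1–6.3%.

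| Other analyses, 20 surgeons | Type I error |
|---|---|
| CMH | 4.8–5.2% (up to 5.5% in a smaller run) |
| Conditional logistic | 4.7–5.2% |
| Random surgeon intercept + location | 5.3–5.4% (Monte Carlo SE 0.3) |
| Location only | 4.5–5.4% |
| Cells under 10 pooled within location | 5.0–5.7% |
| Additive surgeon + location fixed effects | 5.9–6.6% |
| Brachiocephalic cells pooled over surgeons | 5.9–6.6% |

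**5. Effect estimate.** The true odds ratio at 45% vs 65% is (0.65/0.35)/(0.45/0.55) = 2.27, log 0.82. The unconditional cell model gives a median log odds ratio of 0.98, an odds ratio of about 2.7. Without surgeon variation, Mantel-Haenszel gives 2.29 and conditional logistic 2.27.

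**The case against.** The strongest reply is that section 13 is only the basis for the SAP. Factor coding, pooling of small cells and the form of the likelihood are normal SAP content, and that SAP text was not available. The 7% needs three choices that the plan never makes: the full surgeon-by-location cross, one fixed effect per cell, and an unconditional fit without pooling. The surgeon count is also an inference. The synopsis, in its analysis text, speaks of a run-in patient per site, so the 20 run-ins may simply mirror the 20 sites.

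Most of this stands. A reader might infer that the trial's primary test runs at 7%. The documents do not support that, because they do not commit to the fit that produces it. What remains is that the only strata the plan defines lead most directly to that fit, and nothing in the available text rules it out. More surgeons than sites would make the inflation worse.

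A reader might also infer that the stated power is wrong. It is not. Sizing on an unstratified comparison and analysing with adjustment is ordinary practice, and the figures reproduce.

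Finally, an excess of about 2 points matters mainly for borderline results, and at 45% vs 76% the plan has more than 99% power. That limits the practical impact but does not restore the stated level.

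**Conclusion.** The concern holds as a conditional one. The analysis stratum and the handling of sparse cells are undefined in sections 13.3.3 and 13.3.4 and in the synopsis. Under one unconditional fixed effect per surgeon-by-location cell, the two-sided type I error is about 7% with about 20 surgeons, and the median odds ratio is about 2.7 for a true 2.27.

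The size rests on an inferred surgeon count, on assumed block size and surgeon volumes, and on a brachiocephalic share at the plan's 20% ceiling. The direction is the same in every setting tried. Four analyses stay near 5%: CMH, conditional logistic, a random surgeon intercept with location, and location only. Additive surgeon and location fixed effects reduce the inflation but do not remove it.

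This should be fixed before unblinding. Confidence is medium, because the omitted detail may exist in SAP text that was not available.

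**What to change.** In sections 13.3.3 and 13.3.4, the synopsis and the SAP, before unblinding:

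1. Define the analysis stratum and state whether dialysis status at enrollment is part of it.
2. Name a test that holds its level with sparse strata. One choice is a two-sided CMH test or conditional logistic regression on the surgeon-by-location strata, reporting the Mantel-Haenszel or conditional odds ratio. If an ordinary logistic model is preferred, use fistula location with a random surgeon intercept, or location only.
3. Use the same method for the binary secondary endpoints.
4. Optionally, note in section 13.2 that the 82% power and the 45% vs 59% threshold refer to an unstratified two-proportion comparison. Do not add a new power figure, since it would depend on a surgeon count that the plan does not state.

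The cost is wording only, with no change to randomization, data collection or sample size. At 45% vs 65% with about 20 surgeons, CMH has 79–81% power against about 82% unstratified, a loss of roughly 2–3 points. The loss is larger (power 74–77%) with 40 surgeons or with dialysis status crossed. Location only keeps about 82%.

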- Access planning procedures. Duplex ultrasound of the index limb for vascular mapping to determine diameter and depth of the target outflow vein and diameter of the target artery. In subjects with a history of or current use of a catheter ipsilateral to the side where the AV fistula is planned or a pacemaker has been placed in the ipsilateral central vein, a venogram is **strongly recommended** as part of access planning. This approach is consistent with current standard of care.  
*Note: Access planning procedures may be performed/repeated on the day of index procedure to verify individual measurements.*

- Kidney Disease and Quality of Life – Short Form (KDQOL-SF) survey (see [Appendix B](#))

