### **8.1. Inclusion Criteria**

Subjects must meet ALL of the following inclusion criteria to be enrolled in the study:

1. Age of at least 18 years
2. Provide written informed consent using a form that is approved by the Institutional Review Board (IRB)
3. Currently on hemodialysis for  $\leq$ 12 months or expected to initiate hemodialysis within approximately 6 months of the creation of the AV fistula.
4. Life expectancy of at least one year
5. Vascular anatomy suitable for creation of the AV fistula, determined by pre-procedure duplex ultrasound (target artery  $\geq$ 2 mm, target vein  $\geq$ 2.5 mm, and vein depth  $\leq$ 5 mm in the cannulation segment, the latter approximately 10 cm in length)
6. Successful creation of a single-stage radiocephalic or brachiocephalic end-to-side fistula
7. Willing to comply with the specified follow-up evaluations

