# 10. ASSESSMENT OF EFFICACY

## 10.1. Primary Endpoint

The primary endpoint of the study is Fistula Suitability for Dialysis at 6 months (FSD6) defined as a composite of:

- a. For subjects who are on hemodialysis by day 150, suitability for dialysis will be determined by the ability to use the fistula for dialysis using 2-needles with a mean dialysis machine blood pump speed of  $\geq 300$  mL/min for at least two-thirds of the dialysis sessions performed during a 30 day suitability ascertainment period that will commence on day 150.
- b. For subjects who are not on hemodialysis on day of enrollment and who do not initiate hemodialysis by day 150, suitability for dialysis will be determined by a vascular ultrasound performed at the 6 month follow up visit. Suitability for dialysis

will be defined as a fistula with an access vein diameter (AVD) of  $\geq 6$  mm (internal diameter) and an access blood flow of  $\geq 500$  mL/min.

Evaluation of Fistula Suitability for Dialysis at 6 months:

- For subjects undergoing hemodialysis during the suitability ascertainment period, suitability for dialysis will be based on the subject's dialysis session records
- For subjects who are not on hemodialysis on the day of enrollment (i.e. on the day of fistula creation) and who do not initiate hemodialysis by day 150, suitability for dialysis will be based on duplex ultrasound results performed at the 6 month follow up visit.

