### **13.3.4. Secondary Efficacy Endpoints**

Time to event secondary endpoints will be analyzed by stratified log-rank test. Binary endpoints will be compared between treatments via the same logistic regression model as for the primary efficacy endpoints. Continuous secondary endpoints will be compared via analysis of covariance for a model including factors for treatment, strata, and baseline covariate if available, or non-parametric rank tests if normality or homogeneity assumptions appear substantially violated. Overall study-wise type 1 error control across secondary endpoints will be addressed via step-down testing. That is, the secondary endpoints will be tested one at a time in step-down order, until the first non-significant result, after which step-down testing will stop for purposes of supporting conclusions.

Individual patient listings will be provided for the primary and secondary endpoints.

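### The primary FSD6 model leaves out the pre-operative vein and artery diameters that every subject already has: a cheap efficiency not taken, not an error

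*Combined protocol and SAP*

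**What the plan says.** Section 13.3.3 fixes the primary analysis: "the proportions will be compared between treatment and control using a logistic regression model with factors for treatment and stratum". The synopsis agrees: "This endpoint will be analyzed using logistic regression with factors for treatment and stratum". Section 13.3.4 sends the binary secondary endpoints, FSD at 12 months and maturation by Day 90, to the same model. The strata come from Section 9.2.2.2, where subjects are allocated "using permuted block randomization stratified by surgeon and fistula location".

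Inclusion criterion 5 in Section 8.1 requires "Vascular anatomy suitable for creation of the AV fistula, determined by pre-procedure duplex ultrasound", with minimum artery and vein diameters. Section 7.3.1 lists among the required baseline evaluations "Duplex ultrasound of the index limb for vascular mapping to determine diameter and depth of the target outflow vein and diameter of the target artery", and allows these measurements to be repeated on the day of surgery. Randomization follows successful fistula creation, so both diameters are known before allocation.

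The plan does use baseline values elsewhere. For continuous secondary endpoints, Section 13.3.4 specifies "analysis of covariance for a model including factors for treatment, strata, and baseline covariate if available". No efficacy model names either diameter.

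**The concern.** A binary endpoint with about 100 subjects per arm carries limited information. A baseline variable that predicts the outcome recovers some of it if the variable is in the pre-specified model. Here the candidates are complete by design and cost nothing further to collect. They are also plausible predictors: Section 5.1 says in words that dilatation of the vein is what decides suitability. For subjects not on hemodialysis by day 150, Section 10.1 says "suitability for dialysis will be based on duplex ultrasound results performed at the 6 month follow up visit", and one of the two criteria read from that scan is access vein diameter.

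Two things are at stake. One is power in the 45% vs 65% scenario, where the plan has about 82% and little to spare. The other is chance imbalance: randomization is not stratified on vessel size, so one arm may by luck start with smaller vessels. An adjustment for this added after unblinding would be only supportive under Section 13.3.6.

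**Working it through.** **Inputs.** Sections 13.2 and 7.1: N = 200 analysed, taken as 100 per arm (1:1 allocation); two-sided alpha 0.05; FSD6 45% vs 65% (stated power about 82%) and 45% vs 76% (stated power above 99%). Assumption, not in the documents: the prognostic strength of diameter, expressed as an odds ratio (OR) per SD and varied over a range.

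**Step 1: reproduce the plan's figures.** With the pooled two-proportion z-test, power = Φ[(d√n − 1.96√(2p̄(1−p̄))) / √(p₁(1−p₁)+p₂(1−p₂))].

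- 45% vs 65%: (0.20×10 − 1.96×√0.495) / √0.475 = (2.000 − 1.379)/0.689 = 0.901, so power is 81.6%. The unpooled version is Φ(0.20/0.0689 − 1.96) = 82.7%. Both agree with about 82%.
- 45% vs 76%: (3.100 − 1.355)/0.656 = 2.66, so power is 99.6%. This agrees with above 99%.

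**Step 2: add baseline diameter.** Trials were simulated with 100 per arm and a standard normal covariate. The intercepts were solved so that the marginal rates stay at 45% and 65%, and logistic models were fitted with and without the covariate. Stratum terms were left out. Power, without → with adjustment:

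| Assumed OR per SD | One covariate (10,000 trials) | Two covariates, one uninformative |
|---|---|---|
| 1.0 | – | 83.0% → 81.8% |
| 1.6 | 82.8% → 83.6% | 82.5% → 83.7% |
| 2.0 | 83.0% → 85.3% | 83.4% → 86.0% |
| 2.5 | 82.7% → 86.7% | 82.4% → 86.9% |

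A separate run with the likelihood-ratio test (5,000 trials per setting) gave 82.1% → 82.3% at OR 1.25, 83.5% → 83.6% at OR 1.5 and, at the extreme, 81.9% → 88.6% at OR 3. In these simulations without strata, type I error with adjustment stayed at 4.7% to 5.4%.

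**Step 3: express the gain as information.** The ratio of information is [(Φ⁻¹(power with) + 1.96) / (Φ⁻¹(power without) + 1.96)]². For the one-covariate column:

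- OR 1.6: (2.938/2.906)² = 1.02, or 2%, about 4 of 200 subjects.
- OR 2.0: (3.009/2.914)² = 1.07, or 7%, about 13 subjects.
- OR 2.5: (3.072/2.902)² = 1.12, or 12%, about 24 subjects.

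**Step 4: chance imbalance.** The standard error of the difference in mean diameter between arms is √(2/100) = 0.14 SD. In about 16% of trials the treated arm is worse off by at least that much. In those trials, at 45% vs 65%, the unadjusted model has power of about 73%, 68% and 67% (OR 1.6, 2.0, 2.5), against about 83%, 84% and 88% with adjustment.

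**Step 5: how much of the endpoint is vein diameter?** Limb (b) needs diameter ≥6 mm and flow ≥500 mL/min. At least 100 of about 200 evaluable subjects must be on hemodialysis at surgery, so limb (b) covers at most 100/200, about half. It probably covers fewer, because the others are expected to start within about 6 months. Limb (a) is two-needle use at adequate pump speed.

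**The case against.** The strongest reply is that nothing here is wrong. Treatment plus stratum is a valid test of equal proportions, its stated power is correct, and at the base-case rates of 45% vs 76% power is already 99.6%. All of that stands.

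A reader might go further and infer that power is definitely being lost. The documents do not support that. They give no figure for how pre-operative diameter predicts FSD6. The statement in Section 5.1 concerns dilatation after creation, not calibre beforehand. The entry minimums truncate the range of diameters, and fistula location, already a stratum, may carry part of the vessel-size information.

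A reader might also infer that omitting diameter biases the result toward no effect. It does not bias the proportions being compared. The odds ratio is non-collapsible, so the conditional and marginal odds ratios are different quantities. With the same 45% and 65%, the marginal value is (0.65/0.35)/(0.45/0.55) = 2.27, and the conditional value is 2.77 when OR per SD is 3. Nor is pre-operative vein diameter simply the baseline value of the endpoint, for the reasons in Step 5. Chance imbalance is already allowed for in the type I error rate, and the imbalanced trials are part of the average power in Step 2.

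The simulations also omit the strata. A check with an assumed 20 surgeons by 2 locations as fixed effects (simple allocation, 2,000 runs) gave type I error of about 6% to 7% with and without the covariate, and a similar power gain of about 0 to 6 points. The inflation comes from sparse strata rather than from the diameters, but the revised model must deal with it.

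Finally, Section 13.1 defers full detail to an SAP whose text is not in the supplied document, and it may add covariates. That limits confidence, but it does not alter the primary model stated in Section 13.3.3.

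**Conclusion.** The point holds as a cheap improvement of minor severity, with moderate confidence. The primary model omits two baseline measurements that every subject must have before randomization. In the 45% vs 65% case, using them gains about 1 to 5 points of power if the OR per SD is 1.6 to 2.5 (about 2% to 12% more information by the one-covariate figures). It costs about 1 point or less if the OR is 1.0 to 1.3. At 45% vs 76% the gain is practically nil. The range rests on an assumed prognostic strength and on simulations without stratum terms. Protection against an unlucky imbalance in vessel size is a further benefit when diameter is prognostic. The documents do not support calling the planned analysis biased, invalid or underpowered relative to its own statement.

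**What to change.** Before unblinding, amend Section 13.3.3 and the synopsis as follows:

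- Specify the FSD6 model as treatment, the stratification terms, and baseline target-vein and target-artery diameter as continuous covariates. Take the last pre-operative duplex value, since the measurement may be repeated on the day of surgery.
- Use the same model for FSD at 12 months and maturation by Day 90.
- Report the standardised difference in proportions with its 95% CI from this model, because the hypotheses and the power are stated on proportions.
- State how sparse surgeon-by-location strata are handled in that model.
- Keep the model without diameters as a sensitivity analysis.

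The cost is wording in the protocol and SAP, with no new data and no more subjects. The downside is up to about 1 point of power if the diameters turn out not to be prognostic, and a conditional odds ratio with a different meaning, which the standardised difference addresses.
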